5.6. INVESTIGATIONAL DEVICE ACCOUNTABILITY

Documentation of receipt, use and return of all Sphere-9 Ablation Catheters as well as the Affera Mapping and Ablation System must be maintained by the Principal Investigator (PI) or his/her designee. Investigational devices are to be used only in accordance with this protocol and under supervision of the PI or a duly designated person. It is the PI's responsibility to ensure that all study devices are kept in a secure location, with access limited to individuals authorized by the investigator. A record of all study devices received, used and returned must be maintained by the site until the conclusion of the study. Following accountability of the study devices by the Sponsor or its designee, all unused study devices will be returned to the Sponsor/Designee as directed in writing by the Sponsor or designee for gross reconciliation.

5.7. PRIOR AND CONCOMITANT MEDICATION

All concomitant antiarrhythmic drugs (AAD) and other important cardiovascular medications (taken within 30 days of Day 0) will be recorded at each visit. For each medication taken, the following information will be collected:

- Medication trade or generic name;
- Indication for which the medication was given;
- Dose/strength, route, and frequency of administration;
- Date started, and date stopped (or continuation at study exit).

6. EXAMINATIONS AND EVALUATIONS

6.1. EVALUATIONS CONDUCTED AT SCREENING ONLY

6.1.1. **DEMOGRAPHICS**

Date of birth, gender, race and ethnicity will be recorded.

6.1.2. MEDICAL HISTORY

Relevant medical history including duration and frequency of arrhythmia(s), their subsequent treatments (e.g., medications, previous ablation) and associated symptoms will be obtained at Screening. All positive and negative findings will be carefully documented. Any new finding discovered during the Screening evaluation and prior to the index ablation procedure will be considered to be part of the medical history and will not be recorded as an AE.

6.1.3. PHYSICAL EXAM

A physical exam will be performed at Screening. The exam will include the following: head, eyes, ears, nose, and throat (HEENT), heart, lungs, abdomen, extremities, lymph nodes, musculoskeletal, neurological, and gastrointestinal systems. Any abnormalities should be categorized as clinically significant (CS) or not clinically significant (NCS), and the abnormalities should be recorded. Actual height will be measured.

6.1.4. HEMATOLOGY

Laboratory testing will be conducted by a local laboratory at each site at Screening. Hematology evaluation will include: complete blood count (CBC): red blood cells (RBC); hemoglobin (Hgb), hematocrit (HCT), platelets and white blood cells (WBC). Abnormal readings will be considered to be part of the medical history and will not be recorded as an AE.

6.1.5. **PREGNANCY TEST (WOMEN OF CHILDBEARING POTENTIAL ONLY)**

For women of childbearing potential, a urine beta human chorionic gonadotropin (β -HCG) test will be performed at Screening. Results of the test must be negative. Confirmed menopause is defined as postmenopausal for ≥ 1 year.

6.1.6. OPTIONAL CT OR MR IMAGING

At the discretion of the investigator or the principal investigator, computed tomography (CT) or magnetic resonance (MR) imaging may be conducted during screening. Imaging may also be conducted at any time during the follow-up period. Any clinically significant abnormalities will be recorded.

6.2. EVALUATIONS CONDUCTED DURING THE STUDY

6.2.1. 12 LEAD EKG

A 12-lead electrocardiogram (EKG) will be conducted. The EKG recording will be printed out, and a copy will be placed with subject records. Any clinically significant abnormalities will be recorded.

6.2.2. TRANSTHORACIC ECHOCARDIOGRAPHY (TTE)

A TTE will be conducted at Screening, and may be conducted at the physician's discretion prior to Discharge following the ablation procedure if indicated. At screening, measurements will include EF, LV septal wall thickness (AF patients only), estimation of mPAP, and assessment of left atrial thrombus to the extent possible (AF patients only). Prior to Discharge following the ablation procedure, TTE may be used to assess pericardial effusion. Any (structural) abnormalities should be categorized as clinically significant (CS) or not clinically significant (NCS), and the abnormalities should be recorded.

6.2.3. CONCOMITANT MEDICATIONS

Concomitant AADs and other important cardiovascular medications will be recorded at each visit using the trade name or generic name as described in Section 5.7.

6.2.4. VITAL SIGNS

Vital signs consisting of blood pressure (while subject is sitting), temperature, weight, heart rate, and respiratory rate will be measured.

6.2.5. ATRIAL THROMBUS SCREENING

Prior to the ablation procedure, transesophageal echocardiography (TEE) will be the preferred method to assess left atrial thrombus (for left atrial procedures) and spontaneous echo contrast. Alternatively, if the subject has been on continuous anticoagulation for at least 3 weeks prior to the procedure, intracardiac echocardiography (ICE) may be used to assess cardiac thrombus and spontaneous echo contrast. Any abnormalities should be categorized as clinically significant (CS) or not clinically significant (NCS), and the abnormalities should be recorded.

6.2.6. OPTIONAL ENDOSCOPIC EVALUATION OF THE ESOPHAGUS

At the discretion of the investigator, endoscopic evaluation of the esophagus (gastroscopy) may be conducted to evaluate the extent of esophageal ulceration. Any abnormalities should be categorized as clinically significant (CS) or not clinically significant (NCS), and the abnormalities should be recorded.

6.2.7. AMBULATORY CARDIAC MONITORING

Within the Day 90, Day 180, and Day 365 follow-up windows, each subject will be monitored for a minimum of 48 hours with an ambulatory cardiac monitor. Episodes of atrial fibrillation, atrial flutter, or atrial tachycardia lasting longer than 30 seconds will be noted.

7. EVALUATION OF ADVERSE EVENTS AND DEVICE DEFICIENCIES

7.1. ADVERSE EVENTS DEFINITIONS

An **adverse event (AE)** is the development of an untoward medical occurrence or the deterioration of a pre-existing medical condition following or during exposure to an investigational medical device, whether or not considered causally related to the investigational medical device.

An untoward medical condition can be symptoms (e.g., nausea, chest pain), signs (e.g., tachycardia, enlarged liver) or clinically significant abnormal results of an investigation (e.g., laboratory findings, electrocardiogram).

Conditions or diseases that are chronic but stable should not be recorded as an AE. Changes in a chronic condition or disease that are consistent with natural disease progression are NOT considered AEs and should not be recorded. These medical conditions should be adequately documented in the subject's medical history. However, medical conditions present at enrollment that worsen in intensity or frequency in a manner inconsistent with the natural course of the disease during the treatment or post-treatment periods should be reported and recorded as AEs.

A recurrence of the treated arrhythmia requiring hospitalization in order to administer cardioversion prior to the Day 90 visit is within the scope of treatment for chronic but stable AF patients. This will not be considered an adverse event.

A serious adverse event (SAE) is any untoward medical occurrence which:

- Results in death permanent impairment of a body function or permanent damage to a body structure;
- Results in serious deterioration in the subject's health that either:
 - Is life-threatening;
 - Requires inpatient hospitalization (admission to hospital with a stay > 24 hours) or prolongation of hospitalization which is not specifically required by the protocol or is elective;
 - Results in permanent impairment of a body function or permanent damage to a body structure; or
 - Requires medical or surgical intervention to preclude permanent impairment of a body function or permanent damage to a body structure.

Additionally, important medical events that may not result in death, be lifethreatening or require hospitalization may be considered SAEs when they jeopardize the subject or require medical or surgical intervention to prevent one of the serious outcomes listed above.

Adverse device effect (ADE) is an AE related to the use of an investigational medical device. Note, this definition includes AEs resulting from insufficient or inadequate instructions for use, operation, or any malfunction of the investigational medical device.

In addition, this definition includes any event resulting from use error or from intentional misuse of the investigational medical device.

Serious adverse device effect (SADE) is an ADE that that has resulted in any of the consequences characteristic of a SAE.

An **unanticipated adverse device effect** (UADE) is defined as any serious adverse effect on health or safety or any life-threatening problem or death caused by, or associated with, a device, if that effect, problem, or death was not previously identified in nature, severity, or degree of incidence in predicate devices, or any other unanticipated serious problem associated with a device that relates to the rights, safety, or welfare of subjects.

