	After confirmation of the absence of left atrial thrombus precluding catheter introduction, eligible subjects will undergo mapping and ablation. Esophageal evaluation, and CT and/or MR imaging may optionally be performed after treatment or during follow-up.
	Subjects will be followed for 365 days after the ablation procedure to characterize safety and product performance. Note, the Day 10 visit can be conducted by telephone. Ambulatory monitoring will be conducted within the follow-up windows at Day 90, Day 180 and Day 365. Use of antiarrhythmic drugs (AADs) and other important cardiovascular drugs will be collected at every visit. Serious adverse events (AEs) will be collected starting on Day 0 through study exit.
SCHEDULE OF Examinations	Visit 1 - Screening (within 30 days) Visit 2 - Ablation (Day 0) Visit 3 - Day 10 ± 3 days (telephone call) Visit 4 - Day 90 ± 14 days Visit 5 - Day 180 ± 30 days Visit 6 - Day 365 ± 30 days
Study Outcomes	Safety: The primary safety outcome is the rate of the following serious adverse events (SAEs) occurring starting Day 0 and extending through the Day 10 assessment: transient ischemic attack; cerebrovascular accident; major bleeding; cardiac tamponade; pulmonary vein stenosis; severe pericarditis requiring extended hospitalization; myocardial infarction; diaphragmatic paralysis; atrio-esophageal fistula (through the Day 90 assessment); valvular damage; phrenic nerve palsy; intra-procedural device complications requiring surgical intervention; and death.
	 Device performance: The primary product performance outcome is determined during the procedure and is defined as the following: Catheter handling sufficient to reach reasonable intended targets, as determined by the physician: catheter delivery to the desired cardiac chambers manipulation of catheter

	 completion of mapping procedure safe removal of catheter from the subject 3D electro-anatomical map creation and utility sufficient to aid diagnosis Generation of acceptable acute therapeutic RF lesions
	The secondary product performance outcome is freedom from documented recurrence of the treated arrhythmia through the Day 365 post-treatment follow-up visit. In AF subjects, this includes freedom from documented AF, atrial tachycardia (AT), or AFL.

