5.2. STUDY DESIGN

This is a prospective, single-arm, single center study involving the Affera Sphere-9 Ablation Catheter and the Affera Mapping and Ablation System in up to 30 patients. The arrhythmias treated in this study are common atrial arrhythmias: atrial flutter (AFL), paroxysmal atrial fibrillation (AF), and persistent atrial fibrillation.

The primary safety outcome is the rate of the following serious adverse events (SAEs) occurring starting Day 0 and extending through the Day 10 assessment:

transient ischemic attack; cerebrovascular accident; major bleeding; cardiac tamponade; pulmonary vein stenosis; severe pericarditis requiring extended hospitalization; myocardial infarction; diaphragmatic paralysis; atrio-esophageal fistula (through the Day 90 assessment); valvular damage; phrenic nerve palsy; intraprocedural device complications requiring open chest or heart surgery; vascular complications requiring surgical intervention; and death.

The primary product performance outcome is determined during the procedure and includes catheter handling, 3D electro-anatomical map creation and utility sufficient to aid diagnosis, and generation of acceptable acute therapeutic RF lesions.

The secondary product performance outcome is freedom from the treated arrhythmia detected by ambulatory monitoring or ICD interrogation at the Day 90, Day 180, and Day 365 Visits. In AF subjects, this includes freedom from documented AF, AT, or AFL.

Pre-screening, i.e., medical record review without obtaining informed consent, is allowed.

Initial Screening Activities. After providing informed consent, initial screening consisting of review of relevant history including duration and frequency of arrhythmia(s), their subsequent treatments (e.g., medications, previous ablation) and associated symptoms will be performed.

If the subject passes the initial screening, remaining screening tests will be performed which include assessment of study eligibility, demographics, concomitant use of antiarrhythmic drugs (AADs) and other important cardiovascular drugs, physical exam, vital signs, 12 lead EKG, hematology, transthoracic echocardiography (TTE), urine pregnancy test (women of childbearing potential only), and optional CT and/or MR imaging

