7.5. ANTICIPATED ADVERSE EVENTS

Anticipated complications/AEs are defined as complications/events that can be reasonably associated with catheter ablation procedures.

Anticipated AEs include, but are not limited to:

- Air embolism
- Allergic reaction (including anaphylaxis)
- Anesthesia reaction
- Angina
- Aorto-right atrial fistula
- Arrhythmias, including exacerbation of pre-existing atrial fibrillation
- Arterial-venous fistula
- Cardiac perforation/ tamponade
- Cardiac thromboembolism
- Cardiac or respiratory arrest
- Catheter entrapment

- Cerebrovascular incident / Stroke
- Chest pain/discomfort
- Congestive heart failure
- Coronary artery dissection
- Coronary artery spasm
- Coronary artery thrombosis / occlusion
- Death
- Diaphragmatic paralysis
- Dislodgement of ICD or permanent pacing leads
- Endocarditis
- Esophageal ulceration
- Gastroparesis
- Heart failure / pump failure
- Hemoptysis
- Hemoptysis
- Hemothorax
- Hypotension
- Hospitalization (initial and prolonged)
- Increased creatinine phosphokinase (CPK) level
- Infections
- Laceration
- Leakage of air or blood into the lungs or other organs due to perforation
- Left atrial esophageal fistula
- Major bleeding, requiring surgery or transfusion
- Myocardial infarction
- Obstruction or perforation or damage to the vascular system
- Pericarditis
- Pericardial effusion
- Phrenic nerve damage including Diaphragmatic paralysis
- Pleural effusion
- Pneumonia
- Pneumothorax
- Pulmonary edema
- Pulmonary embolism
- Pulmonary vein dissection
- Pulmonary vein thrombus
- Pulmonary hypertension
- Respiratory depression
- Skin burns
- Severe PV stenosis or complete occlusion, even asymptomatic
- Tamponade, potentially requiring surgery
- Temperature elevation or fever
- Transient Ischemic Attack (TIA)
- Thromboembolism

- Thrombosis
- Unintended complete or incomplete AV, Sinus node, or other heart block or damage
- Valve damage
- Vascular bleeding / local hematomas / ecchymosis
- Vasovagal reactions
- Ventricular tachyarrhythmia
- Volume overload

7.6. **DEVICE DEFICIENCIES**

Device deficiency is defined as an inadequacy of a medical device with respect to its identity, quality, durability, reliability, safety or performance.

Note, device deficiencies include malfunctions, use errors, and inadequate labelling. All device deficiencies or malfunctions that occur during the course of the trial and could have led to an SAE must be reported, whether or not they were associated with an AE.

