8.2.2. DEVICE PERFORMANCE

The primary product performance outcome is determined during the procedure, and is defined as the following:

- Catheter handling sufficient to reach reasonable intended targets, as determined by the physician:
 - catheter delivery to the desired cardiac chambers
 - manipulation of catheter
 - completion of mapping procedure
 - o safe removal of catheter from the subject
- 3D electro-anatomical map creation and utility sufficient to aid diagnosis
- Generation of acceptable acute therapeutic RF lesions

The secondary product performance outcome is freedom from documented recurrence of the treated arrhythmia detected by ambulatory monitoring at the Day 90, Day 180, and Day 365 Visits. In AF subjects, this includes freedom from documented recurrence of AF, AT, or AFL. Recurrence is defined as any episode lasting longer than 30 seconds.

8.3. **Descriptive Analyses**

Continuous variables will be summarized using standard quantitative statistics: number of non-missing observations, mean, standard deviation, median, quartiles and range (minimum and maximum observed values). The number of missing observations, if any, will also be summarized.

Categorical variables will be summarized using classical frequency statistics: number of non-missing observations and percentages by categories. Number and percent of missing data, if any, will also be summarized.

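### Three conflicting definitions of recurrence let a subject cardioverted before the first monitoring window count as recurrence-free under Section 8.2.2, with no adverse event recorded

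*Combined protocol and SAP*

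**What the plan says.** The secondary performance outcome appears in three places:

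- Study Synopsis, Study Outcomes: "freedom from documented recurrence of the treated arrhythmia through the Day 365 post-treatment follow-up visit". No means of detection is specified.
- Section 5.2: "freedom from the treated arrhythmia detected by ambulatory monitoring or ICD interrogation at the Day 90, Day 180, and Day 365 Visits".
- Section 8.2.2: recurrence "detected by ambulatory monitoring at the Day 90, Day 180, and Day 365 Visits", with an episode counting if it lasts more than 30 seconds.

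None of the three states a blanking period.

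Section 7.1 separately takes one kind of early recurrence out of adverse event reporting. The event is "A recurrence of the treated arrhythmia requiring hospitalization in order to administer cardioversion prior to the Day 90 visit". The reason given is that it "is within the scope of treatment for chronic but stable AF patients", and the consequence is: "This will not be considered an adverse event". The rule opens with the treated arrhythmia in general, but its reason names AF patients only. Section 5.3.1 also admits subjects with typical atrial flutter.

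Section 6.2.7 requires at least 48 hours of ambulatory monitoring within each of the Day 90, Day 180 and Day 365 windows. Section 5.4.6 sets the first window at 90 ± 14 days. It also lists episodes of the treated arrhythmia over 30 seconds as an item apart from the monitoring, without a look-back period or a source.

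**The concern.** The study rationale (Section 1.1) is that nondurable lesions lead to recurrence. An early recurrence that needs a hospital admission bears directly on that question. Section 8.2.2 is the definition an analyst would normally follow. Read literally, it does not see an event that begins and ends before the first recording, and Section 7.1 keeps the same event out of the adverse event data. The Synopsis would count it. The reported freedom rate therefore depends on which section is followed, and the narrower definition can only give the more favourable figure.

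**Working it through.** The plan states no expected recurrence rate, hypothesis or derived sample size (Section 8.1), so there is no planned figure to reproduce. The check compares the definitions and then sizes the difference.

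**1. One subject under each definition.** Take a subject whose treated arrhythmia recurs, who is admitted and cardioverted before Day 76, and whose three recordings are all clean.

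| Source | What counts | This subject |
|---|---|---|
| Study Synopsis | any documented recurrence through Day 365 | recurrence |
| Section 5.2 | monitoring or ICD interrogation at three visits | recurrence only if an ICD record exists and is counted |
| Section 8.2.2 | ambulatory monitoring at three visits | recurrence-free |
| Section 7.1 | adverse event status | not an adverse event |

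Any event counted under Section 8.2.2 is counted under Section 5.2, and any event counted there is counted under the Synopsis. So, for the same data, freedom (8.2.2) ≥ freedom (5.2) ≥ freedom (Synopsis). The direction is fixed.

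**2. The time left unobserved.**
- The first window opens on Day 90 − 14 = Day 76. An event that is over before then cannot appear on protocol-required monitoring.
- The Section 7.1 exclusion ends at the Day 90 visit, so it can run to Day 90 + 14 = Day 104. From Day 76 until the visit, an event is seen only if it coincides with the recording.
- Minimum required monitoring is 3 × 48 = 144 hours out of 365 × 24 = 8,760 hours: 144 / 8,760 = 1.6% of the year.

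**3. Size per subject.** With n treated subjects (up to 30, Section 5.3), moving k subjects from recurrence to recurrence-free raises the freedom rate by 100 × k / n points. At n = 30:
- k = 1: 3.3 points
- k = 3: 10.0 points
- k = 5: 16.7 points

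With fewer subjects the step is larger; at n = 20 it would be 100 / 20 = 5.0 points each.

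**4. Chance that it arises at all.** The documents give no rate, so p is assumed: the proportion of subjects with such an admission and three clean recordings. The chance of at least one in 30 is 1 − (1 − p)^30.

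| Assumed p | Expected number (30p) | Chance of at least one |
|---|---|---|
| 2% | 0.6 | 45% |
| 5% | 1.5 | 79% |
| 10% | 3 | 96% |
| 20% | 6 | 99.9% |

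**5. Effect on safety reporting.** The primary safety outcome (Section 8.2.1) is a closed list of named serious events through Day 10, with atrio-esophageal fistula through Day 90. Recurrence is not on the list, so Section 7.1 cannot change that rate. The effect is confined to the general AE/SAE listings. The visit lists and Appendix 1 collect serious events, so it arises only for admissions that would otherwise be serious. The hospitalization criterion in Section 7.1 requires a stay of more than 24 hours, sits under serious deterioration in health, and carries a qualifier about elective admissions.

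**The case against.** The strongest case on the other side has five parts.

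- **The event need not vanish.** The Synopsis counts it. ICD interrogation under Section 5.2 might show it. The separate episode item at the Day 90 visit, or a drug change recorded under Section 5.7, might leave a trace. This stands, and it rules out the inference that such an event is absent from every outcome. It does not close the gap: the episode item is not linked to Section 8.2.2, cardioversion is not among the data that Section 5.7 collects, and most of these routes are only possibilities.
- **The primary safety result is untouched.** This stands in full. A reader might infer that safety as a whole is made to look better; the documents support only the limited effect on listings shown above.
- **Sections 7.1 and 7.5 do not contradict each other.** Section 7.5 lists "Arrhythmias, including exacerbation of pre-existing atrial fibrillation" as anticipated, and Section 7.1 removes one defined subset. A general list with a stated exception is coherent, and the revision table shows that the exclusion was intended. This stands.
- **Early recurrence may not be treatment failure.** Section 7.1 places it within the scope of treatment. But no section sets a blanking period for the performance outcome, so the plan does not settle the matter. Reporting from both starting points avoids having to settle it here.
- **The study is descriptive.** No threshold or test depends on the rate. True, but the rate is the result that will be reported, and readers need to know what it counts.

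**Conclusion.** The point holds as a conflict between definitions with a one-directional effect. Under Section 8.2.2, and under Section 5.2 without an ICD record, a subject admitted and cardioverted before Day 76 with three clean recordings is counted as recurrence-free and has no adverse event. Under the Synopsis the same subject is a failure. Each such subject is worth 3.3 percentage points at n = 30. The total is unknown, because the documents give no rate of early cardioversion; the 3.3, 10.0 and 16.7 points for 1, 3 and 5 subjects are illustrations. The conclusion rests on reading Section 8.2.2 literally and on the affected subjects having clean recordings at all three visits.

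It does not extend to the primary safety rate, to a contradiction between Sections 7.1 and 7.5, or to a finding that recurrence before Day 90 must be treated as failure. Whether the Section 7.1 exclusion applies to AFL subjects is left open by its wording.

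**What to change.** - Use one definition in the Synopsis, Section 5.2 and Section 8.2.2: any documented episode longer than 30 seconds, by any means of detection, through Day 365. Keep the existing rule that AF, AT and AFL all count in AF subjects.
- Report freedom from recurrence twice, from Day 0 and from the Day 90 visit, so that early events are visible without a choice on blanking.
- Keep the Section 7.1 classification if wanted, but record every arrhythmia admission or cardioversion from Day 0 with its date. Tabulate these separately (n, %) for AF and AFL subjects.
- State in Section 7.1 whether the exclusion applies to AFL subjects.

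The cost is matching edits in three places, one clarification, one CRF item, one additional table entry and one extra analysis. The freedom figure may come out slightly less favourable than under Section 8.2.2 as written.
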